Visit window			Day 3 after first inj	Day 7 after first inj	±3 days	±3 days	±3 days	±3 days	Day 3 after last inj	Day 7 after last inj	±3 days	±3 days	±3 days	
Previous (excluding disease-specific) and concomitant medication	X	X	X	X	X	X	X	X	X	X	X	X	X	6.8
Adverse events	X	X	X	X	X	X	X	X	X	X	X	X	X	8.4

Abbreviations: 6M=6-month formulation; AE=adverse event; ALT=alanine aminotransaminase; AST=aspartate aminotransaminase; eCRF=electronic case report form; ECG=electrocardiogram; ECOG= Eastern Cooperative Oncology Group; EoS=end of study; Hb=haemoglobin, inj=injection; M=month; PSA=prostate-specific antigen WBC=white blood cell

- a If necessary, participants can request home visits, except for visits where study intervention is to be administered.
- b Height to be collected at screening only.
- c ECG to be assessed as clinically indicated at any other time during the study as required.
- d All testosterone assessments to be performed using the central laboratory, except at screening. At screening, testosterone to be assessed up to 7 days prior to Day 1 using the local laboratory. On Day 1 and Day 169, samples for testosterone to be collected pre-dose.
- e An imaging scan is not required if performed within 6 months of study screening.
- f Haematology (WBC and differential count, platelet count, Hb), blood chemistry (creatinine, glucose, ALT, AST, alkaline phosphatase, total and conjugated bilirubin). Glucose: Non-fasting levels in all participants.
- g Injection site to be specifically checked for local site injection reactions 2 hours after study intervention administration. Any local reaction AEs will be collected on the eCRF.

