4.2 Scientific Rationale for Study Design

This phase III, single-arm, open-label study will investigate the efficacy and safety of triptorelin 6-month formulation administered subcutaneously in participants with prostate cancer previously treated and castrated with a GnRH analogue.

The non-comparative, open-label clinical study design is acceptable as the primary endpoint will assess testosterone levels by the percentage of participants maintaining castrate levels of serum testosterone (defined as $<1.735 \text{ nmol/L (50 ng/dL)}$ during the study (primary endpoint, as outlined in [Table 3](#)).

Assessment of testosterone is a well-established and a widely used efficacy parameter in studies investigating hormone deprivation therapies in patients with prostate cancer. Demonstration of testosterone castration $<1.735 \text{ nmol/L (50 ng/dL)}$ as an endpoint is also compliant with the European Medicines Agency (EMA) and European Association of Urology guidelines [[Mottet 2021](#)].

Some patients with prostate cancer, particularly those who are elderly and/or receiving anticoagulants, are at a higher risk of developing haematomas or excessive bleeding following intramuscular injection (see Summary of Product Characteristics). Thus, subcutaneous injection may be a better option.

As presented in Section [2.2](#), a clinical study was conducted with triptorelin embonate 22.5 mg (6-month formulation) administered subcutaneously in participants with advanced prostate cancer who were non-castrated. However, the primary endpoint regarding the maintenance rate of castration was not met, as maintenance of castration was not observed after the first injection in some participants but maintained for all participants after the second injection. The present study aims to assess whether castration maintenance is achieved via subcutaneous administration in participants already castrated at the beginning of the study. Thus, the outcomes of this study intend to fulfil an unmet need and improve treatment convenience.

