7.2 Participant Discontinuation/Withdrawal from the Study

- A participant may withdraw from the study at any time at his own request or may be withdrawn at any time at the discretion of the investigator for safety, behavioural or compliance reasons.
- At the time of discontinuing from the study, if possible, an early discontinuation visit should be conducted, as shown in the SoA. See SoA for data to be collected at the time of study discontinuation and for any further evaluations that need to be completed.
- The reason for discontinuation will be recorded in the eCRF.
- If the participant withdraws consent for disclosure of future information, the sponsor may retain and continue to use any data collected before such withdrawal of consent.
- If the participant requests to discontinue the study intervention, they will be asked to be followed for the study procedures.
- If the participant withdraws consent for any further contact, the investigator will explain in the medical records as to whether the withdrawal is only from further receipt of study intervention or also from study procedures. This information must be entered in the eCRF.
- If a participant withdraws from the study, he may request destruction of any samples taken and not tested, and the investigator must document this in the site study records.
- A participant will be withdrawn from the study if they have inadequate testosterone suppression (defined as >50 ng/dL detected at least 30 days after the first administration of study intervention and on two consecutive measurements at least 2 weeks apart, at either a scheduled or unscheduled study visit).

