
 To demonstrate the effect of triptorelin embonate 22.5 mg 6-month formulation administered subcutaneously to suppress the 'acute-on-chronic' effect following the administration of the second dose 	
 Percentage of participants castrated on Day 3 and Day 7 after each injection administered on Day 1 and Day 169 (castration defined as testosterone <1.735 nmol/L (50 ng/dL))

 To demonstrate the effect of triptorelin embonate 22.5 mg 6-month formulation administered subcutaneously in the maintenance of PSA 	
 Percent change in PSA from baseline (prior to injection) at Day 169 and Day 337 (Percent change in PSA defined as the absolute value of difference between the PSA values at Day 169 and Day 337 and the baseline value divided by the baseline value)

Associated Procedure / Instruction Reference	319480-SOP
Form Reference	080091-FOR v7.0

Objectives	Endpoints

 To demonstrate the safety profile of triptorelin embonate 22.5mg 6-month formulation administered subcutaneously 	
 Incidence of TEAEs (including local tolerability) throughout the study i.e. up to Day 337 Change from baseline in clinical safety laboratory parameters (blood chemistry and haematology) at Day 337 Change from baseline in physical examination at Day 169 and Day 337 Change from baseline in ECG at Day 337 Change from baseline in vital signs (blood pressure and heart rate) at each visit up to Day 337

AE=adverse event; ECG=electrocardiogram; PSA=prostate-specific antigen; TEAE=treatment-emergent adverse event

Note: A list of laboratory parameters to be assessed during the study are presented in Protocol Appendix 10.2.

- Hypotheses**

Hypotheses for this study are defined below.

The primary objective of this study is to evaluate the efficacy triptorelin embonate 22.5 mg (6-month formulation) administered subcutaneously in maintaining serum testosterone castrate levels during the study (maintenance of castration defined as testosterone <1.735 nmol/L (50 ng/dL) at Day 29, Day 85, Day 141, Day 169, Day 253, Day 309 and Day 337) with two complete study intervention administrations. Thus, the null hypothesis to be tested is as follows:

Null hypothesis: percentage of participants castrated (serum level of testosterone <1.735 nmol/L) from date of first dose to Day 337 is less than or equal to 90%.

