4 ANALYSIS SETS

Screened Set

The screened set will contain all participants who signed an informed consent for this study. In case of re-screening, the participant will be counted once only in the screened set. The previous site and assigned subject numbers will be collected to link the first and second screening data.

Enrolled Set

The enrolled set will contain all participants who were enrolled to study treatment. A participant will be considered as enrolled if he has signed the informed consent form and is assigned to treatment.

Intent-to-Treat Set

The intent-to-treat (ITT) Set will contain all participants who signed an informed consent form and received at least one administration of study intervention and have a serum testosterone level <1.735 nmol/L (50 ng/dL) on Day 1 (pre-dose measurement).

Full Analysis Set

The full analysis set (FAS) will contain all participants who signed an informed consent form and received two administrations of study intervention and completed all visits for testosterone measurement (Day 29, Day 85, Day 141, Day 169, Day 253, Day 309 and Day 337). Note, a participant will be included in the FAS if his testosterone measurement is ≥ 50 ng/dl before the end of treatment, end of study or withdrawn from study, whichever is earlier.

Per Protocol Set

The per protocol (PP) set will contain all participants from the FAS who did not experience any major protocol deviations that may interfere with efficacy evaluation (refer to section 5.3 for details regarding the management of deviations).

Safety Set

The safety set will contain all participants who receive at least one dose of study intervention.

Associated Procedure / Instruction Reference	319480-SOP
Form Reference	080091-FOR v7.0

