5.1.2 Descriptive Statistics

Due to the single-arm nature of the study, all statistical analyses will be descriptive. All raw and derived variables will be listed and described using summary statistics. For categorical variables, summary statistics will be displayed using descriptive statistics by frequency count and percentages by category. The missing category will be presented if applicable. Unless otherwise specified, participants with missing data will be included in the calculation of percentages. For quantitative variables, summary statistics will be displayed using descriptive statistics by number of observations, mean, standard deviation (SD), first quartile, median, third quartile, minimum and maximum. Frequency and proportion of missing data will be displayed.

Associated Procedure / Instruction Reference	319480-SOP
Form Reference	080091-FOR v7.0

For the efficacy analyses, the descriptive statistics of treatment effects and corresponding 95% CIs for the primary endpoint and secondary endpoints will be presented if applicable.

5.1.3 *Baseline Value*

Unless otherwise specified, baseline is defined as the last non-missing measurement taken prior to first Investigational Medicinal Product (IMP) administration (including unscheduled assessments).

5.1.4 *Reference Start Date and Study Day*

Reference start date is defined as the day of the first IMP administration.

The day of the first IMP administration will be Day 1. Study day will be calculated as:

- The difference between the event date and the reference date plus one day, if the event is on or after the reference date.
- The difference between the event date and the reference date, if the date of event is prior to the reference date.

Study day will appear in any listings where an assessment date or event date appears.

In case of partial or missing event date, study day will appear missing while any associated durations will be presented based on the imputations described in [Appendix 2](#).

5.2 **Enrolment, Disposition and Analysis Sets**

A Listing presenting study treatment dispensation details will be provided (Listing 16.1.7).

Following disposition summaries will be provided:

- Summary table with the number and percentage of participants screened, screen failed, reason for screen failures, enrolled, treated, having completed the study, withdrawn and reason for withdrawal,
- Summary table with the number and percentage of participants enrolled per visit,

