5.7.3 Analysis of Key Secondary Efficacy Endpoints

5.7.3.1 Secondary Efficacy Endpoints

The secondary efficacy endpoints are listed below:

- Percentage of participants castrated at each timepoint on Day 29, Day 85, Day 141, Day 169, Day 253, Day 309 and Day 337 (castration defined as testosterone <1.735 nmol/L (50 ng/dL))
- Percentage of participants with a serum testosterone level <0.694 nmol/L (20 ng/dL) during the study
- Percentage of participants with a serum testosterone level <0.69 nmol/L (20 ng/dL) at each timepoint on Day 29, Day 85, Day 141, Day 169, Day 253, Day 309 and Day 337
- Percentage of participants castrated on Day 3 and Day 7 after each injection administered on Day 1 and Day 169 (castration defined as testosterone <1.735 nmol/L (50 ng/dL))
- Percent change in PSA from baseline (prior to injection) at Day 169 and Day 337 (Percent change in PSA defined as the absolute value of difference between the PSA values at Day 169 and Day 337 and the baseline value divided by the baseline value).

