Appendix 3 Programming Convention for Outputs

Associated Procedure / Instruction Reference	319480-SOP
Form Reference	080091-FOR v7.0

IPSEN GROUP

CONFIDENTIAL

D-FR-52014-245

SAP Final: Version 1.0: 30 January 2023

PAGE 39/43

A3 Programming Convention for Outputs

All text fields must be left justified and numeric or numeric with some text specification (e.g.: not done, unknown, <4.5, ...) must be decimal justified.

The mean, median, lower quartile, upper quartile, SD, and 95% CI values will be reported to one decimal place greater than the raw data recorded in the database.

The minimum and maximum values will be reported with the same number of decimal places as the raw data recorded in the database.

In general, the maximum number of decimal places reported should be four for any summary statistic.

Percentages will be presented to one decimal place. Percentages will not be presented for zero counts. Unless otherwise specified, percentage will be calculated using N as denominator. The denominator will be specified in a footnote for clarification if necessary. If sample sizes are small, the data displays will show the percentages, but in the CSR only frequency counts should be described.

All values below or above a limit of detection (e.g. <0.1 or >100) will be listed as such.

Dates will be presented in the format [ddmmmyyyy] and times in the format [hh:mm].

Associated Procedure / Instruction Reference	319480-SOP
Form Reference	080091-FOR v7.0

IPSEN GROUP

CONFIDENTIAL

D-FR-52014-245

SAP Final: Version 1.0: 30 January 2023

PAGE 40/43

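### The Day 171/175 castration rate has no at-risk condition, so it can mix loss of castration before dose two with an effect of dose two

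*SAP*

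**What the plan says.** The objective in SAP 2.1 (Table 1) is "to suppress the 'acute-on-chronic' effect following the administration of the second dose". The matching endpoint, in SAP 5.7.3.1 and Protocol section 3, is "Percentage of participants castrated on Day 3 and Day 7 after each injection administered on Day 1 and Day 169", with castration meaning testosterone below 50 ng/dL. SAP 5.7.3.2 analyses the secondary endpoints in the FAS with the primary estimand's intercurrent-event strategies. Nothing there refers to the value before the injection.

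Four other provisions decide who is in the denominator:

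- **FAS Note (SAP 4).** Beyond men with two injections and all seven primary visits, "a participant will be included in the FAS if his testosterone measurement is ≥ 50 ng/dl before the end of treatment" (or before end of study or withdrawal, whichever is earlier). ICE 1 to 3 in SAP 5.7.2.1 set aside only men without such a value.
- **Percentages.** SAP 5.1.2 says that, by default, "participants with missing data will be included in the calculation of percentages", and also that a missing category is presented where applicable. Appendix 3 adds: "Unless otherwise specified, percentage will be calculated using N as denominator".
- **Withdrawal (Protocol 7.2).** "A participant will be withdrawn from the study if they have inadequate testosterone suppression", defined as more than 50 ng/dL on two consecutive measurements at least 2 weeks apart, from 30 days after the first dose.
- **Sampling (Protocol 1.3, note d).** "On Day 1 and Day 169, samples for testosterone to be collected pre-dose".

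**The concern.** An acute-on-chronic effect is a rise in a man who is castrate when he is re-dosed. Two kinds of men cannot show one, yet can lower the percentage castrated on Day 171 and Day 175: men who lost castration before the second injection and have not regained it, and men who left before that injection. If either group is present, the figure offered for the objective partly measures loss of castration during the first dosing interval. A reader could then attribute to dose two something that happened before it.

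The background in Protocol 4.2 gives some reason to care. In the previous subcutaneous study of this formulation, "maintenance of castration was not observed after the first injection in some participants but maintained for all participants after the second injection". Those men were non-castrate at entry, so the parallel is loose.

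**Working it through.** **1. Can a man already non-castrate be dosed and counted?** Yes. The Day 169 sample is taken before the injection. If it is his first value ≥50 ng/dL, he does not have two consecutive high values and does not meet the Protocol 7.2 rule. He is in the FAS. If he is still ≥50 on Day 171 or 175, the endpoint's own definition counts him as not castrated.

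**2. Can an undosed man be in the denominator?** By default, yes. On scheduled visits, values above 50 at both Day 85 and Day 141 meet the withdrawal rule before Day 169. The FAS Note keeps such a man in the FAS, and ICE 1 to 3 do not set him aside. His Day 171/175 windows in SAP 6.1 are counted from the second injection date, so he has none. With N as denominator and missing data included, he is in the denominator and cannot be in the numerator.

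**3. Does Day 1 have the same gap?** In principle. Eligibility rests on a local-laboratory value up to 7 days before Day 1. The ITT set requires a Day 1 pre-dose value below 50; the FAS does not.

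**4. The plan's own figures.** No figure is given for this endpoint. The illustration borrows N = 130 and 97% from SAP 2.3, and these reproduce. With n = 130 the exact test against 90% needs at least 124 castrate men:

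- P(X ≥ 124 | 130, 0.90) = 0.0207, below 0.025
- P(X ≥ 124 | 130, 0.97) = 0.903, the stated power of about 90%
- 130 / (1 − 0.10) = 144.4, rounded up to 145

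**5. Size, with assumed counts.** Expected failures are 0.03 × 130 = 3.9, taken as 4. Let u be FAS men without dose two, b men ≥50 before dose two and still ≥50 after, and s true surges. The numerator is c = 130 − u − b − s. Intervals are Clopper-Pearson: lower limit Beta(0.025; x, n − x + 1), upper limit Beta(0.975; x + 1, n − x). When x = n the lower limit is 0.025^(1/n); for n = 126 this is 97.1%.

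| u, b, s | c/130 | Dosed: c/(130 − u) | Dosed and castrate pre-dose: c/(130 − u − b) |
|---|---|---|---|
| 0, 0, 0 | 100% (97.2 to 100) | 100% | 100% |
| 4, 0, 0 | 126/130 = 96.9% (92.3 to 99.2) | 126/126 = 100% | 126/126 = 100% (97.1 to 100) |
| 0, 4, 0 | 126/130 = 96.9% (92.3 to 99.2) | 126/130 = 96.9% | 126/126 = 100% (97.1 to 100) |
| 2, 2, 0 | 126/130 = 96.9% (92.3 to 99.2) | 126/128 = 98.4% (94.5 to 99.8) | 126/126 = 100% (97.1 to 100) |
| 0, 6, 0 | 124/130 = 95.4% (90.2 to 98.3) | 124/130 = 95.4% | 124/124 = 100% (97.1 to 100) |
| 0, 4, 2 | 124/130 = 95.4% (90.2 to 98.3) | 124/130 = 95.4% | 124/126 = 98.4% (94.4 to 99.8) |

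Restricting to dosed men removes u but not b. Only the last column isolates a new rise.

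**6. Do the planned Day 169 and Day 171 rates, side by side, settle it?** Not within a man. Suppose all 130 are dosed and both days read 126/130. This fits four men non-castrate on both days and no surge, giving 126/126 = 100% among men at risk. It also fits four men non-castrate on Day 169 who recover while four others rise, giving 122/126 = 96.8%.

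**The case against.** The strongest reply is that the endpoint is scored as the protocol defines it. A man at ≥50 ng/dL on Day 171 is not castrated, and the plan reports a percentage castrated, not a count of surges. A reader might infer that the plan counts undosed men as surge failures. The documents do not support that. No section classes them so: the missing-category provision would show them as missing, the endpoint's reference to each injection administered can be read as covering dosed men only, and the windows after dose two do not exist without it. Appendix 3 also allows a footnote on the denominator, and the table shells are a separate document. For these men the denominator is unspecified, not wrongly specified.

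A reader might also infer that every first-interval failure is reported as a second-dose surge. That fails too: a man who is castrate again by Day 171 counts as castrated.

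The Day 169 rate is a planned secondary endpoint and all efficacy data are listed, so an attentive reader would see if the rate did not fall between Day 169 and Day 171. That helps, but step 6 shows that two marginal rates cannot say whether the same men are involved.

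Finally, the Protocol 4.2 study reported castration maintained in all participants after the second injection, which argues against assuming that nobody recovers. The illustration is therefore an upper case for four failures. A rate limited to men castrate on Day 169 also conditions on a post-baseline response, so it should stand beside the protocol endpoint and not replace it.

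**Conclusion.** The point holds in limited form, as a minor one. The endpoint has no at-risk condition, so the rate after dose two can combine earlier loss of castration with an effect of the injection. For men non-castrate before and after dose two this follows from the endpoint's definition. For undosed men it follows only from general table defaults.

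The shift is 130/130 minus 126/130, about 3 percentage points, if there are four such men and no true surge. It ranges from 0 to 4.6 points (6/130) for zero to six such men. These counts are assumptions; the documents give none. Any distortion lowers the reported rate, so it runs against the product. The endpoint is descriptive with no success threshold, and the primary analysis and sample size are untouched.

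**What to change.** In SAP 5.7.3.1 and 5.7.3.2:

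- Keep the protocol endpoint, and state its Day 171/175 denominator as men who received the second injection.
- Add, for each injection, the percentage still below 50 ng/dL among men who received that injection and were below 50 ng/dL in that day's pre-dose central-laboratory sample, with an exact 95% CI.
- Report on separate lines the numbers not dosed, ≥50 ng/dL pre-dose, and with a missing post-dose sample. Say whether the last group stays in the denominator of the added rate.

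The cost is SAP wording, one derived flag and one more table row. All the samples are already scheduled. The added rate has a slightly smaller denominator and is conditioned on pre-dose status, which a footnote should say.

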2.6 Change from Statistical Section of the Protocol

There is no change from the statistical section of the protocol.

Associated Procedure / Instruction Reference	319480-SOP
Form Reference	080091-FOR v7.0

IPSEN GROUP

CONFIDENTIAL

D-FR-52014-245

SAP Final: Version 1.0: 30 January 2023

PAGE 11/43

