5.7 Efficacy

5.7.1 General Considerations

The FAS set will be used for efficacy analyses unless explicitly stated differently.

A listing of all efficacy data (raw and derived) will be provided (see listing detail conventions in [Appendix 4](#)).

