5.7.3.2 Main Secondary Analysis

The same strategies as those for the primary estimand will be used for the main secondary analysis in the FAS, with castration maintenance criteria being replaced with 0.694 nmol/L (20 ng/dL) whenever applicable.

For binary secondary endpoints, including castration maintenance (<50 ng/dL) rate at specific timepoints, castration maintenance (<20 ng/dL) rate during the study, castration maintenance (<20 ng/dL) rate at each timepoint, castration maintenance rate along with the associated 95% exact CI will be provided. For percent change in PSA from baseline at Day 169 and Day 337, descriptive statistics will be provided.

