7 DERIVED DATA

The following derived data will be calculated and included in the listings:

(1) Baseline value

Baseline value is defined as the last non-missing measurement taken prior to first IMP administration (including unscheduled assessments) (see section [5.1.3](#)).

(2) Duration of subject participation (study exposure)

Study exposure will be calculated as:

Study exposure (days) = last assessment or visit performed – informed consent date +1. It will be then divided by 30.4375 to be presented in months.

(3) Age

Subject age (years) will be as collected in eCRF.

(4) BMI

BMI (kg/m^2) will be derived as $\text{Weight} (\text{kg})/[\text{Height}(\text{cm})/100]^2$ and rounded to the nearest decimal.

(5) Time from diagnosis to screening

Time from diagnosis to screening will be calculated as (date of screening – date of diagnosis). It will be then divided by 30.4375 to be presented in months.

In case of missing screening day, the day will be imputed to 15. In case of missing screening month, the month will not be imputed.

In the same way, in case of missing diagnosis day, the day will be imputed to 15. In case of missing diagnosis month, the month will not be imputed.

No imputation will be performed for missing year.

(6) Compliance

Compliance will be calculated as:

Dose administered divided by dose planned to be administered multiplied by 100. The percentage of residual will be considered to determine the percentage of dose non-administered, and so the dose administered.

A total of two injections will be considered as planned dose administration in this study.

Associated Procedure / Instruction Reference	319480-SOP
Form Reference	080091-FOR v7.0

IPSEN GROUP

CONFIDENTIAL

D-FR-52014-245

SAP Final: Version 1.0: 30 January 2023

PAGE 27/43

(7) Percent change from baseline

Percent change from baseline will be calculated as:

$((\text{assessment at the visit} - \text{assessment at baseline}) / \text{assessment at baseline}) * 100$.

Zero will be used if both assessment at baseline and change from baseline are zero.

(8) Changes from baseline

Changes from baseline will be calculated as a difference from baseline (e.g. assessment at the visit – assessment at baseline).

(9) Study drug exposure

Study drug exposure will be calculated as:

Study drug exposure (days) = last study drug administration date – first study drug administration date +1. It will be then divided by 30.4375 to be presented in months.

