Appendix 1 List of PCSA Criteria

Associated Procedure / Instruction Reference	319480-SOP
Form Reference	080091-FOR v7.0

IPSEN GROUP

CONFIDENTIAL

D-FR-52014-245

SAP Final: Version 1.0: 30 January 2023

PAGE 33/43

A1. List of PCSA Criteria

PCSA for Vital Signs parameters:

Parameter	PCSA
Systolic Blood Pressure	≤ 90 mmHg and change from baseline ≤ -20 mmHg ≥ 180 mmHg and change from baseline ≥ 20 mmHg
Diastolic Blood Pressure	≤ 50 mmHg and change from baseline ≤ -15 mmHg ≥ 105 mmHg and change from baseline ≥ 15 mmHg
Heart Rate	≤ 50 bpm and change from baseline ≤ -15 bpm ≥ 120 bpm and change from baseline ≥ 15 bpm

PCSA for ECG parameters (source ICH E14):

Parameter	PCSA
QTc	$]450; 480]$ msec $]480; 500]$ msec >500 msec
Delta QTc	$]30;60]$ msec increase from baseline >60 msec increase from baseline

PCSA for Weight from Physical Examination parameters:

Parameter	PCSA
Weight	$\leq -5\%$ change from baseline $\geq 5\%$ change from baseline

Associated Procedure / Instruction Reference	319480-SOP
Form Reference	080091-FOR v7.0

IPSEN GROUP

CONFIDENTIAL

D-FR-52014-245

SAP Final: Version 1.0: 30 January 2023

PAGE 34/43

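### The PSA endpoint is defined as an absolute change, so its summary cannot tell a rise from a fall, and the SAP's general percent-change rule conflicts with it

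*SAP*

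**What the plan says.** The objective is to show an effect in maintaining PSA. The endpoint is percent change in PSA from baseline at Day 169 and Day 337. The Schedule of Activities (Protocol 1.3) collects PSA only on Day 1, Day 169 and Day 337 or early discontinuation, and this is the only PSA efficacy endpoint.

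SAP 5.7.3.1 gives the formula: "Percent change in PSA defined as the absolute value of difference between the PSA values" at each of those visits and at baseline, then divided by baseline. SAP Table 1, the synopsis in Protocol 1.1 and Protocol Table 3 define it the same way. None of the four writes a factor of 100.

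SAP Section 7, item (7), defines percent change from baseline in general as visit minus baseline, over baseline, times 100. It keeps the sign and adds one special case: "Zero will be used if both assessment at baseline and change from baseline are zero". PSA is neither named nor exempted.

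The analysis text in SAP 5.7.3.2 cites neither formula: "For percent change in PSA from baseline at Day 169 and Day 337, descriptive statistics will be provided". SAP 2.6 states "There is no change from the statistical section of the protocol". SAP Section 8 lists three changes (hypothesis wording, the ITT set, multiple imputation), none about PSA.

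**The concern.** There are two linked defects.

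First, the PSA-specific formula discards direction. In advanced prostate cancer a rise and a fall in PSA mean different things, and the protocol's own inclusion criterion 2 treats rising PSA after failed local therapy as meaningful. An endpoint meant to describe maintenance of PSA should show which way it moved. Absolute change shows only how far participants moved.

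Second, two formulas stand side by side without an order of precedence. Two programmers, each following the SAP, could produce different tables under the same title, one unsigned and possibly on a 0-to-1 scale, the other signed and in percent.

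At stake is the readability of one reported secondary endpoint, which the SAP places under its key secondary heading. The primary endpoint does not depend on it.

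**Working it through.** The documents give no figure that rests on this definition, so there is nothing to reproduce. The check applies both formulas to the same values. Write B for baseline PSA and V for PSA at the visit.

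- PSA-specific rule (SAP 5.7.3.1): |V - B| / B
- General rule (SAP Section 7, item (7)): 100 × (V - B) / B

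**One participant, illustrative B = 2**

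| V | PSA-specific rule | General rule |
|---|---|---|
| 1 | \|1 - 2\| / 2 = 0.5 | 100 × (1 - 2) / 2 = -50% |
| 3 | \|3 - 2\| / 2 = 0.5 | 100 × (3 - 2) / 2 = +50% |

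**One hundred participants, all with B = 2**

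| Outcome | Absolute mean and median | Signed mean and median |
|---|---|---|
| All fall to 1 | 0.5 | -50% |
| All rise to 3 | 0.5 | +50% |
| Half fall to 1, half rise to 3 | 0.5 | 0% (quartiles -50% and +50%) |

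The absolute summary is the same in all three cases. The signed mean and median separate them, and the signed quartiles show that the zero in the last row hides offsetting movement.

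**A spread of changes.** Five participants fall by 10, 20, 30, 40 and 50%; another five rise by the same amounts. In percentage points, the absolute mean is 30, the median 30 and the quartiles 20 and 40 in both groups. The signed medians are -30 and +30.

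**No systematic change.** The documents give no SD for PSA change, so the SDs here are assumptions shown over a range.

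Normal change with mean 0 and SD s, in percentage points: mean |X| = s × √(2/π) and median |X| = 0.6745 × s.

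| s | Absolute mean | Absolute median | Signed mean and median |
|---|---|---|---|
| 10 | 8.0 | 6.7 | 0 |
| 30 | 23.9 | 20.2 | 0 |
| 50 | 39.9 | 33.7 | 0 |

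PSA ratios are usually skewed, so the check was repeated with V/B log-normal, median 1 and log SD σ. Absolute figures come from 4,000,000 simulated draws. Signed quartiles are 100 × (exp(±0.6745σ) - 1) and the signed mean is 100 × (exp(σ²/2) - 1).

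| σ | Absolute mean | Absolute median | Signed median | Signed quartiles | Signed mean |
|---|---|---|---|---|---|
| 0.1 | 8.0 | 6.7 | 0 | -6.5, 7.0 | 0.5 |
| 0.3 | 24.7 | 20.0 | 0 | -18.3, 22.4 | 4.6 |
| 0.5 | 43.4 | 32.7 | 0 | -28.6, 40.1 | 13.3 |

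The absolute median is well above zero although the typical participant has not changed. With skewed ratios the signed mean also drifts upward, so the median and quartiles are the better summary of signed change.

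**The case against.** **The specific definition overrides the general one.** The SAP repeats the PSA formula twice, in agreement with the protocol, and introduces Section 7 as derived data for listings. Item (7) has other uses: the weight criteria in SAP Appendix 1 ("PCSA for Weight from Physical Examination parameters") are signed percent changes. The statement in SAP 2.6 adds little, because the PSA definition sits outside the protocol's statistical section, and an unchanged definition needs no entry in Section 8. This is a reasonable reading and weakens the charge of ambiguity. It does not help with direction: if the PSA formula governs, the endpoint is unsigned.

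**Direction is available elsewhere.** SAP 5.1.2 says "All raw and derived variables will be listed and described using summary statistics" and SAP 5.7.1 says "A listing of all efficacy data (raw and derived) will be provided". Section 7, item (8), also defines a signed change from baseline. This stands and limits the harm. But raw summaries by visit do not show the distribution of relative change within participants, and the named endpoint is what will be reported.

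**Absolute deviation suits maintenance.** It does measure stability. However, neither document gives that rationale or sets a tolerance around baseline, and the measure treats a halving and a 50% rise as equal.

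**The factor of 100 is presentational.** Agreed. The word percent implies it; the absolute value is the substantive fault.

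**The size illustrations are assumed.** Also agreed. The normal model with SD 50 puts about 2.3% of participants below -100%, which PSA cannot reach. If at least half of participants were exactly unchanged, the absolute median would be 0. The single-participant example needs no such assumption.

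**Conclusion.** The concern holds. As written, the PSA endpoint gives the same value for a rise and a fall of equal relative size, and the general rule in the SAP gives a different answer. Settling precedence in favour of the PSA wording would remove the ambiguity but leave the loss of direction.

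The loss of direction follows from the formula and rests on no assumption. How far the absolute summary sits above zero when nothing has changed systematically does depend on assumed variability: a median of roughly 7 to 34 percentage points over the ranges tried, against a signed median of 0.

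The consequence is confined to one descriptive secondary endpoint. SAP 5.7.1.1 plans no formal testing of efficacy, so no error rate, sample size or primary conclusion changes. It should be corrected, but it does not threaten the trial.

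**What to change.** Before database lock:

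1. In SAP Table 1 and SAP 5.7.3.1, define the endpoint as 100 × (PSA at visit - PSA at baseline) / PSA at baseline, with reference to Section 7, item (7).
2. Record the change and its reason in SAP Section 8.
3. In SAP 5.7.3.2, name the median and quartiles of the signed change as the summary to report. SAP 5.1.2 already plans them for quantitative variables.
4. State how a zero baseline with a non-zero visit value is handled. Item (7) covers only the case where baseline and change are both zero.
5. If absolute change is still wanted as a measure of stability, keep it as an additional summary labelled as such.

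Align Protocol 1.1 and Protocol Table 3 at the next amendment; the Section 8 entry documents the difference until then.

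The cost is low: one definition in two places of the SAP, one Section 8 entry and a short clarification. The signed derivation already exists and no new data are needed. The protocol wording carries whatever ethics review that amendment needs. If the database is already locked, SAP Section 1 requires deviations from the SAP to be documented in the clinical study report, and the change should be reported there.
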